Aim 3: Assess preliminary effectiveness by comparing the two study arms on the following outcomes at 6-months post-randomization: a) proportion of patients with A1C $<$ 8%; b) proportion of patients with an A1C test; c) number of emergency department visits; d) primary care visit no-show rate; and e) percent of on-time pharmacy refills for diabetes-related medications.

Phase 3

Aim 1: Extract clinical data on Asian American, Pacific Islander, Native Hawaiian, and Alaska Native populations in KPNW from the EHR as preliminary data for a future grant proposal including these populations in a large-scale, pragmatic, randomized trial aimed to address disparities in diabetes management in relation to socioeconomic needs.

3. Background

Racial/ethnic minorities and low-income individuals in the U.S. are less likely to achieve diabetes-related clinical targets. Only 42% of African Americans and 38% of Hispanics with diabetes have hemoglobin A1C

levels at target ($\leq 7\%$), compared to 58% of Whites.¹ In addition, individuals with low socioeconomic status (of all racial/ethnic backgrounds) are also more likely to have suboptimal diabetes management.^{1,2} This is troubling because poor diabetes management leads to an increased risk for diabetes complications including cardiovascular disease events, contributing to the disparities in the rates of these major diseases.³ As such, pragmatic, multifactorial interventions to address these disparities in diabetes management are sorely needed.

Disparities in diabetes management have been linked to social determinants of health. Social and economic needs, including food insecurity, housing instability, and trouble paying for medical care, are common among racial/ethnic minorities and low-income populations.³ These needs interfere with adequate diabetes self-management behaviors, including healthy eating, physical activity, self-monitoring of blood glucose, and medication adherence,⁴⁻⁹ and are associated with high diabetes-related health care utilization.^{4,10-12} A recent meta-analysis indicated that diabetes self-management interventions are effective for reducing A1C by an average of 0.31% among racial/ethnic minorities,¹³ but access to these interventions is limited partly due to social determinants of health such as lack of transportation to attend sessions or access to the internet for online programs.^{14,15}

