For Phase 1, the study team will conduct a data-only study to determine the number of eligible patients from Kaiser Permanente Northwest (KPNW) and the most common clinic service area where these patients receive primary care. Results from this data-only study will inform Phase 2, which is a RCT. We plan to extract the following variables from the EHR:

[figure not shown]
- Demographics
- Contact information
- Zip code
- Clinic paneled to
- Primary language spoken
- Any Mental health diagnoses
- Health care utilization
 - Outpatient encounters
 - Inpatient encounters
 - ED visits
 - Navigator visit
- Vital Signs
- Labs
- Medical diagnosis
- Existing YCLS data from the VDW
- Social diagnosis codes
- Insurance coverage

For Phase 2, the study team will utilize the KPNW EPIC system to identify potentially eligible patients who meet study criteria. The study team aims to enroll 100 participants and randomize 50 participants to each study arm. After eligible patients have been identified, using REDCap, we will send targeted emails and for those who do not have an email address listed, we will send targeted letters via regular mail. The email/letter will provide an overview of the study and provide the study number for potential participants to call-in and enroll if eligible. One week after sending the emails/letters, bilingual recruitment staff will contact potential participants by phone to follow-up on the email/letter and describe the study and enroll those interested. If study staff are made aware that an interested participant will be unreachable (i.e., out of town) after randomization, the individual will not be randomized until their schedule permits availability to participate in the study, applicable for both study arms. After consent has been captured, enrolled participants will be randomized to one of the study arms. Enrolled participants will receive a thorough explanation of what the randomization process entails, as well as the differences between the two study arms. Data collection, which consists of the administration of the Your Current Life Situation (YCLS) will occur at the Baseline and 6-month follow-up calls. During the Baseline call, study participants will also be provided with contact information to the 211info organization to serve as an additional contact for helping individuals navigate and connect with local resources.

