**Addressing Social Determinants of Health & Diabetes Self-Management
in Vulnerable Populations**

STATISTICAL ANALYSIS PLAN

NCT# 03802825

Date: April 21, 2021 (Published version)

Statistical and Qualitative Analysis Plan

Before we carry out any analyses, we will audit the data for quality and completeness, and evaluate missing data patterns. We will examine variable distributions for outliers and assess them to ensure that they meet the assumptions of the planned analysis. We will present the baseline characteristics as means and standard deviations for continuous variables and as percentages for categorical variables. Nominal variables will be coded as categorical variables for inclusion as predictors in multivariate analyses. All inferential tests will be carried out at a two-tailed alpha level of .05. We will examine group differences on important baseline factors using a student t- test (or the nonparametric Mann-Whitney U test) for continuous variables and chi-square test (or the Fisher's exact test) for categorical variables. Significant variables will be included as covariates in the models.

Recruitment and retention rate, proportion of participants with a successful referral to a patient navigator and CHW, mean number of days to connect each participant to a navigator and CHW, and proportion of participants with unmet basic needs met at 6-month follow-up will be calculated as described in Table 1. For the qualitative analysis, a coding dictionary will be developed based on review of the transcripts' content and interview questions. Codes will denote content of questions, TICD and PRISM domains, and concepts naturally emerging from the discussions. During the coding process, inter-rater reliability will be established by comparing the agreement in coded text with 20% of the transcripts between two coders. Any differences in coding will be resolved through discussion, and the two coders will meet regularly to discuss and refine the coding process. A qualitative database will be compiled, coded, and analyzed using a qualitative software program (Dedoose). Once all transcripts are coded within the software program, we will use text retrieval and grouping functions on specific codes and combinations of

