between the diabetes medication being dispensed and the previous supply running out. Delayed refills will be defined as medication not being dispensed for 7 days or more after the previous supply ran out. For each participant, number of delays or gaps in refills and number of days without a refill will be calculated. Both no-show visit rate and number of delays in refills are continuous variables. We will summarize the distributions with means, medians, standard deviations, and quartiles for each study arm. Assuming normal distribution, we will use the two-sample t-tests to compare the means of these two outcomes between the two study arms. We will use multiple linear regression modeling to examine the association between study arms and these two outcomes. Based on expectations of fairly well-balanced study arms for these two outcomes we will adjust for all unbalanced factors in the models. We will report the coefficients and the 95% CIs associated with the study arm binary variable.

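### The SAP starts the refill-delay clock at supply run-out and has no rule for a supply that ran out before randomisation, so pre-trial days and lapses can enter the refill outcomes as noise

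*SAP*

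**What the plan says.** The last paragraph of the SAP takes refill time as the number of days "between the diabetes medication being dispensed and the previous supply running out". It then sets the threshold: "Delayed refills will be defined as medication not being dispensed for 7 days or more after the previous supply ran out". Two measures follow: "For each participant, number of delays or gaps in refills and number of days without a refill will be calculated".

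Only one of them goes on to formal analysis. The SAP says "Both no-show visit rate and number of delays in refills are continuous variables", and for that pair "we will use the two-sample t-tests to compare the means of these two outcomes between the two study arms", followed by multiple linear regression adjusted for factors found unbalanced. Days without a refill has no between-arm test named for it.

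The no-show rate, defined in the same paragraph, is tied to the 6-month follow-up period. The refill sentences name neither a window nor randomisation. Protocol section 2 (Phase 2, Aim 3) lists the refill outcome as "percent of on-time pharmacy refills for diabetes-related medications" among outcomes compared 6 months after randomisation. That implies a post-randomisation outcome but does not settle a gap that begins before day 0 and ends after it.

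**The concern.** A participant whose supply ran out two months before randomisation and who refills on day 2 has a post-randomisation dispensing. By the SAP's definition, its delay runs back to the pre-trial run-out date. A programmer following the text would score one delay and about 60 days, none of which the assigned arm could have prevented apart from the last two.

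Such gaps are plausible here. Protocol section 5 requires a most recent A1C of at least 8 and at least one social or economic need, and section 3 links such needs to poor medication adherence. The documents do not say how many participants would be without supply at randomisation.

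At stake is the precision of one preliminary effectiveness outcome in a pilot that is meant to inform a larger trial. The SD of a refill measure inflated by pre-trial days would be a poor input to that trial's design.

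**Working it through.** **No figure to reproduce.** The documents state no refill rate, SD, effect size or power. From them come the sample size ("The study team aims to enroll 100 participants and randomize 50 participants to each study arm", Protocol section 6) and the test level ("All inferential tests will be carried out at a two-tailed alpha level of .05", SAP). All other inputs below are assumptions.

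**1. Direction.** Let a share q of each arm carry an open lapse into the trial, each adding one delay. Randomisation gives both arms the same expected q, so the expected difference in mean delays is unchanged. In 20,000 simulated trials with 50 per arm, Poisson mean 1.25 and q = 0.25 in both arms, the t-test rejected in 5.1%. The lapse adds variance, not bias.

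**2. Number of delays (tested), one drug.** Assume Poisson delays with average mean m. Then SD = √(m + q(1−q)).
- Means 1.0 v 0.5, m = 0.75. At q = 0, SD = 0.866 and power is 82%. At q = 0.25, SD = √(0.75 + 0.1875) = 0.968 and power is 73%. At q = 0.10 and 0.50, power is 78% and 71%.
- Means 1.5 v 1.0: 61% at q = 0, then 58%, 55% and 53% at q = 0.10, 0.25 and 0.50.
- Means 2.0 v 1.4: 63%, then 61%, 59% and 58%.

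The loss is 2 to 12 points. If two drugs always lapse together, the added variance is 4q(1−q), and the first case falls from 82% to 66%, 53% and 47%.

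**3. What truncation does to the count.** The q = 0 rows describe removing carried-in lapses altogether. Starting the clock at randomisation does less, because a lapsed participant who restarts on day 8 or on day 150 still scores one delay. Only first-week restarts change. Assume 30% lapsed and monthly restart of 15% (navigation only) v 40% (navigation plus training), at constant hazard. First-week restart is 1 − 0.85^(7/30) = 3.7% v 1 − 0.60^(7/30) = 11.2%. The shift between arms is 0.30 × (0.112 − 0.037) = 0.02 delays.

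**4. Simulation of both measures.** Added assumptions: run-out uniform over 7-180 days before randomisation, one drug, 30-day fills, 10% chance of a lapse at each fill, open gaps counted.
- Days without a refill, 30% lapsed: SD 92 literally and 57 from randomisation. The raw difference is about 26 days either way, and the standardised difference is 0.28 v 0.45. At 20% and 40% lapsed it is 0.25 v 0.39 and 0.30 v 0.50.
- Information kept under the literal rule is the squared ratio: (0.25/0.39)² = 0.41, (0.28/0.45)² = 0.39, (0.30/0.50)² = 0.36.
- Number of delays, 30% lapsed: SD 0.63 literally and 0.62 from randomisation.
- Adjusting the count for lapse at baseline lowers its residual SD by about 13-19% at 20-40% lapsed, a variance reduction of 1 − 0.87² = 24% to 1 − 0.81² = 34%. On the truncated count the SD reduction is about 10-15%. Varying the lapse chance per fill from 5% to 15% widens these ranges to 9-31% and 7-26%.

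**5. A second check on days.** Assume a 10-day difference, in-window SD 25, and exponential pre-trial days with mean μ for a share q. The variance is 625 + 2qμ² − (qμ)². With μ = 60 and q = 0.10 this is 625 + 720 − 36 = 1,309, SD 36.2. Power falls from 52% to 28%, and to 19% and 14% at q = 0.25 and 0.50. With μ = 30 it is 43%, 35% and 28%; with μ = 120 it is 14%, 9% and 7%.

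**The case against.** The strongest reply is that the documents nowhere order pre-trial days to be counted. Aim 3 frames the outcome as post-randomisation, and a sensible analyst might cut gaps at day 0 unprompted. This stands against any claim that the SAP prescribes the pre-trial count: the fault is a missing rule. It does not remove the point, because limiting which dispensings count does not say where the interval before the first of them begins.

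The reply also notes that the large losses concern a measure with no named test, that every rate is assumed, and that refills are the last of five preliminary outcomes in a pilot with no power claim. Poor follow-up is described in the protocol as missed primary care visits, not lapsed medication, and it is absent from the Phase 2 inclusion list. All of this stands and limits the weight of the point.

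A reader might infer from the days figures that pre-trial lapses overwhelm the treatment comparison. The documents do not support that: they give no rates, the raw difference is unchanged, and the tested count loses little with one drug.

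A reader might also infer a bias against the better arm, since a time to refill needs a dispensing to close it. On that reading a lapsed participant who never restarts would score nothing. With six-month restart of 1 − 0.85⁶ = 62% v 1 − 0.60⁶ = 95% and 30% lapsed, that would add 0.30 × 0.33 = 0.10 delays to the arm that restarts more people. But the SAP defines a delay by medication not being dispensed, which an unclosed gap satisfies, and nothing says such gaps score zero. One sentence in the SAP would close this off.

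**Conclusion.** The point holds as an unspecified rule that can add noise. The SAP anchors refill delay on the run-out date and does not say what happens when that date precedes randomisation. The effect is non-differential.

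If 20-40% of participants are lapsed at baseline, the literal rule keeps only about 36-41% of the information in days without a refill, a measure that is calculated but not formally tested. For the tested number of delays the effect is small with one drug, and becomes large only if several drugs lapse together. Truncation alone hardly changes that count; the useful gain is from the baseline covariate. These sizes depend on assumed lapse, restart and run-out patterns; the missing rule does not.

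**What to change.** Add to the refill paragraph of the SAP:
- The refill window opens at randomisation and closes at 6 months.
- Supply on hand at day 0 is carried forward from a dispensing look-back.
- A gap open at day 0 contributes only its post-randomisation days, and the 7-day threshold is applied to those days.
- A gap still open at 6 months counts, with its days up to that date.
- Supply lapsed at randomisation (yes or no) is a pre-specified covariate in the refill regression, whether or not the arms differ on it. Under the present rule it would enter only if found unbalanced.

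The cost is SAP wording and the look-back. Protocol section 5b says the data warehouse already holds pharmacy fills, so no new data collection is needed.

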KPNW is a non-profit, group model integrated health care system that provides comprehensive prepaid health care to its more than 550,000 members in southwest Washington and northwest Oregon. It owns and operates two hospitals, contracts with six other local hospitals, and maintains 22 medical clinics (17 with primary care). All patient contacts within the system and all services referred outside are recorded in a single, comprehensive electronic health record (EHR, KP HealthConnect, based on Epic[®]) that has been in place since 1996. Health and health care utilization data is stored in the Virtual Data Warehouse (VDW), which is maintained by the Kaiser Permanente Center for Health Research. The VDW provides a standardized, distributed data warehouse for the EHR and other clinical and administrative informatics systems employed by the health system. The VDW includes files for all encounters (outpatient and inpatient), vital signs, pharmacy fill data, problem lists and encounter diagnoses, procedures, and laboratory results.

c. Informed Consent Waiver and HIPAA Privacy Rule Waiver of Authorization

Because Phase 1 is a data-only study, we request a waiver of written and signed consent as well as HIPAA authorization for the study to extract participant data from the EHR (e.g., demographics, primary language spoken, contact information, clinic paneled to, vital signs, labs, diagnoses, encounters). At enrollment KPNW members are informed that their medical records may be used for research and that they may choose to opt out of such research; CHR maintains a registry of members who have asked not to be included in research or to have their records used, or both.

For Phase 2, we also request a waiver of written and signed consent as well as HIPAA authorization. Verbal informed consent by the participant will be captured and recorded in REDCap by study staff during the initial recruitment call and after study eligibility has been determined. No study activities or data collection will be gathered until after verbal informed consent has been obtained.

For Phase 3, we are also requesting a waiver of written consent as well as HIPAA authorization for the study to extract participant data from the EHR (e.g., demographics, clinic, primary language spoken, medical diagnosis, most recent A1C, most recent blood pressure measurement, BMI, insurance coverage, existing YCLS data, and social diagnosis codes).

6. Procedures

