codes for a particular topic and summarize the issues, agreements, and disagreements in the content for each item. This process will result in a list of themes relating to intervention acceptability[42] and determinants (barriers and facilitators) of implementation and sustainability. As we summarize and interpret, we will identify findings or patterns among themes and will review data for statements that directly confirm or discredit our interpretations.[43-45]

To assess preliminary effectiveness, using a chi-square test, we will compare the two study arms on proportion of participants with A1C < 8% at 6-month follow-up. In addition, we will conduct a logistic regression analysis to assess the association between the study arms and A1C < 8% at 6-month follow-up, coding the study arms as a binary variable (Navigation only as the reference) as the predictor of interest. We will control for factors that are not balanced between the two arms (e.g., age, sex) in the model. We will conduct similar analyses for the binary outcome, A1C test completed (yes or no).

To analyze the number of emergency department (ED) visits by each participant, we will count and then summarize the distribution of the ED count with means, medians, standard deviations, quartiles, frequency, and proportion of participants with 0, 1, 2+ ED visits, by study arm. We will use the Poisson model (or negative binomial model when appropriate) to analyze the relationship between study arms and the number of ED visits adjusting for the covariates that are significantly different between the two arms. We will report the estimated rate ratio (RR) associated with the study arm binary variable and the 95% CI.

The primary care no-show visit rate will be calculated as the number of primary care visits a participant missed divided by the total number of primary care visits scheduled during the 6-month follow-up period. The time to refill a medication will be based on number of days

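### Aim 3(e) is a percentage of refills dispensed on time, but the SAP tests a count of delayed refills with no number of refills due, so the stated outcome is not produced

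*SAP*

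**What the plan says.** Protocol section 2 (Objectives, Phase 2, Aim 3) lists five outcomes to be compared between arms at 6 months. Item (e) is the "percent of on-time pharmacy refills for diabetes-related medications".

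The SAP handles refills in its closing paragraph. It sets the delay rule: "Delayed refills will be defined as medication not being dispensed for 7 days or more after the previous supply ran out". It then says that, for each participant, the "number of delays or gaps in refills and number of days without a refill will be calculated". Only the first of these two quantities goes forward to the comparison: "Both no-show visit rate and number of delays in refills are continuous variables", and "we will use the two-sample t-tests to compare the means of these two outcomes between the two study arms", followed by multiple linear regression adjusted for unbalanced factors.

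The outcome analysed alongside it, the primary care no-show rate, does have a denominator. Missed visits are "divided by the total number of primary care visits scheduled during the 6-month follow-up period". The refill outcome has no counterpart to this.

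The SAP cites a Table 1, which is not in the text available, only in the sentence on feasibility measures, which ends: "proportion of participants with unmet basic needs met at 6-month follow-up will be calculated as described in Table 1".

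**The concern.** A percentage has a numerator and a denominator, and the SAP supplies only the complement of the numerator. A count of delays depends on how promptly a participant refills and also on how many refills fall due in 6 months. The second depends on days of supply per fill and on the number of diabetes medicines, and the documents fix neither.

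Two things are at stake. If the SAP is followed exactly, the trial reports a different quantity from the one Aim 3(e) names. And because this pilot is meant to inform a full-scale trial, a number that mixes refill timeliness with refill frequency could be carried forward as if it were the protocol's adherence measure.

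**Working it through.** The documents give no refill rate, supply length, standard deviation or power for this outcome, so there is no plan figure to reproduce. The check has two parts.

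**1. The texts side by side**

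| Element | Protocol Aim 3(e) | SAP |
|---|---|---|
| Unit | percentage on time | number of delays |
| Definition of late | none | 7 days or more after run-out |
| Refills due | implied by a percentage | not defined |
| Variable tested | the percentage | the delay count |
| Also calculated | – | days without a refill (no test named) |

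The SAP contains no percentage on time, no total of refills due and no offset.

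**2. When the count can stand in for the percentage**

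Let *d* be delays and *n* refills due. Then percent on time = 100 × (1 − *d*/*n*). If *n* is the same for everyone, ranking by *d* is the exact reverse of ranking by percent. If *n* varies, it need not be.

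Assumed inputs, none from the documents: 182 days of follow-up, one medicine filled on day 0, supply of 30, 60 or 90 days, and a refill counted as due only if its 7-day window closes before follow-up ends. With prompt refilling this gives:
- 30-day supply: due on days 30, 60, 90, 120 and 150, so *n* = 5
- 60-day supply: due on days 60 and 120, so *n* = 2
- 90-day supply: due on day 90, so *n* = 1

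*Same percentage, different counts.* At 75% on time, expected delays are 5 × 0.25 = 1.25, 2 × 0.25 = 0.50 and 1 × 0.25 = 0.25.

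*Opposite ranking, with both participants still refilling.*
- Participant A, 90-day supply: due day 90, filled day 98 (8 days late). *d* = 1, *n* = 1, percent = 100 × (1 − 1/1) = 0%.
- Participant B, 30-day supply: due day 30, filled day 38; due day 68, filled day 76; then on time on days 106, 136 and 166. *d* = 2, *n* = 5, percent = 100 × (1 − 2/5) = 60%.

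The count puts A ahead of B (1 against 2 delays). The percentage puts B ahead of A (60% against 0%).

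*How often this could happen.* Random pairs of participants were simulated with mean 75% on time and within-participant correlation of 0, 0.1 or 0.3. Among pairs whose percentages differ:

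| Refills due (assumed, equal mix) | Count ranks them in opposite order | Count ties them |
|---|---|---|
| all 5 | 0% | 0% |
| 5, 2, 1 | 5% to 7% | 7% to 12% |
| 1, 2, 5, 10, 15 | 10% to 17% | 6% to 9% |

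The last mix stands for several medicines per person. No figure in the documents supports or excludes any of the three.

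*Does the existing test suit the percentage?* With no true difference, the same mix of schedules in both arms and 50 per arm, the two-sample t-test on the per-participant percentage rejects in about 5% of simulated trials under these mixes.

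**The case against.** The strongest reply is that the protocol gives only a short phrase, with no definition of on time and no denominator, and that its Study Design section describes the same domain simply as medication adherence. The SAP, dated April 2021, is the proper place to make such a phrase operational. A 7-day rule, a delay count and days without a refill all measure refill timeliness, so the construct is reported even if the unit differs. This stands in part: it would be too strong to say that refill adherence goes unreported. But the SAP does not say that the count replaces the percentage, or why, and it gives the neighbouring no-show rate an explicit denominator.

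It may also be said that Table 1 could hold the missing definition. Its contents cannot be checked, so the point is limited to the SAP text. That text cites the table only for feasibility measures and writes out the refill definitions without reference to it.

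Finally, randomization should balance refill schedules, so the count comparison is a fair one. This stands. With the same schedule mix in both arms, the count also rejects in about 5% of trials under no difference. In illustrative comparisons of 70% with 80% on time, neither measure is uniformly better: with the 5/2/1 mix, detection was 34% for the percentage against 36% for the count at correlation 0, and 28% against 24% at correlation 0.3.

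**Conclusion.** The mismatch is real and can be read directly from the two documents: Aim 3(e) names a percentage, and the SAP text computes and tests a count that cannot be converted to it without refills due. It should be fixed, but its weight is modest. It touches one of five preliminary-effectiveness outcomes in a feasibility pilot of 100. The existence of the mismatch needs no assumption; every figure for its size rests on assumed supply lengths, numbers of refills and lateness, and the ranking problem vanishes if everyone has the same number due.

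Two stronger readings are not supported.
- A reader might infer that the count test is biased between arms. Rejection does rise if unequal refills due are imposed: with 30% of refills late in both arms, means of 6 against 9 due give 84.8% rejection, while 6 against 6 gives 5.7%. But nothing in the documents suggests such an imbalance, and randomization makes schedules equal in expectation at baseline.
- A reader might infer that a participant who stops refilling would score better than one who is persistently a little late. That depends on treating an unfinished gap as a single delay, which the SAP does not state. The SAP also calculates days without a refill, which would partly show the difference.

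**What to change.** In the SAP, replace the delay count as the tested refill outcome with, for each participant, on-time refills divided by refills due in the 6 months, both summed over that participant's diabetes-related medicines. On time means dispensed less than 7 days after the previous supply ran out, the complement of the SAP's delay rule. Keep the two-sample t-test and the adjusted linear regression. Report the delay count and days without a refill descriptively by arm, with no added test.

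Two conventions need stating, applied identically in both arms.
- A refill that is never dispensed counts as due and not on time, so that stopping does not remove it from the denominator. For example, two on-time 30-day refills followed by stopping would be 2/2 = 100% if only dispensed refills counted.
- One rule fixes how many refills a long gap counts as, including when refilling resumes. Take a 30-day supply with the first refill on day 92 and on-time refills on days 122 and 152. This is 2/3 = 67% if the gap is one late refill, and 2/5 = 40% if each of the three intervals in the gap (days 30, 60 and 90) counts as due and not on time. Either can be defended, but the SAP must choose.

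The cost is a few sentences and a short derivation from the run-out and dispensing dates the SAP already needs. There are three downsides:
- Participants with no refills due have no value. They should be reported by arm, and the number analysed may fall below the number randomized.
- A participant with one refill due weighs as much as one with many.
- The data listed under Setting in the protocol include "vital signs, pharmacy fill data, problem lists and encounter diagnoses, procedures, and laboratory results", with no mention of discontinuation records. If none exist, a medicine stopped by the prescriber may count as not on time, and this should be stated as a limitation.
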